12. REPORTING

The clinical study report will contain at least the following information:

- a) Product identifier and expected SPF
- b) Subject information (number, Fitzpatrick skin phototype, ITA^o value, age and gender)
- c) Characterization of the UV source (% RCEE compliance and intensity in units of radiant flux)
- d) Reference sunscreen used
- e) Individual MED for unprotected skin, test product protected skin and reference sunscreen protected skin
- f) Individual SPF_i values expressed to one decimal place, including all valid data and rejected data for the test product and for the reference sunscreen
- g) Mean SPF values, standard deviation on the mean and 95% CI of the test product and reference formulation
- h) Protocol deviations, if any
- i) Identification, by subject, of the technician who conducted the test
- j) Date of the test
- k) PI signature page to confirm the study was conducted in compliance with this protocol and any amendments, the Principles of GCP and the Declaration of Helsinki.

The clinical study report will be authored by GSKCH and statistical analyses overseen by a member of the GSKCH Biostatistics and Data Management team. GSKCH may commission a professional medical writing service to support the reporting process. The PI will review the clinical study report to ensure the report accurately reflects the way the study was conducted. The PI will sign a page to confirm the study was conducted in compliance with the protocol, the Principles of GCP and the Declaration of Helsinki.

 GlaxoSmithKline	Document Name	207640 Protocol.doc		
	Type	Version	Document Identifier	Effective Date
	eldo_controlled	2.0; Most-Recent; Effective; CURRENT	090032d580d3df08	11-May-2017 13:45:31
	Reason For Issue	Auto Issue		

13. APPENDICES

13.1. Appendix 1 - Abbreviations

AE	Adverse Event
°C	Degrees Celsius
CD	Compact Disc
CI	Confidence Interval
CIE	International Commission on Illumination
CRF	Case Report Form
cm	Centimeter
cm ²	Square Centimeter
EDC	Electronic Data Capture
g	Gram
GCP	Good Clinical Practice
GSKCH	GlaxoSmithKline Consumer Healthcare
h	Hour
ICH	International Conference on Harmonisation of Technical Requirements for Registration of Pharmaceuticals for Human Use
IEC	Independent Ethics Committee
ISO	International Standards Organisation
ITA°	Individual Typology Angle
ITT	Intention to Treat
J	Joule
LSLV	Last Subject, Last Visit
m	Meter
m ²	Square Meter
MED	Minimal Erythema Dose
MEDu	Minimal Erythema Dose of Unprotected Skin
MEDp	Minimal Erythema Dose of Protected Skin
mg	Milligram
mJ	Millijoule
mm	Millimeter
nm	Nanometer
PI	Principal Investigator
PII	Personally Identifiable Information
PP	Per Protocol
RCEE	Relative Cumulative Erythema Effectiveness
SAE	Serious Adverse Event
SEM	Standard Error of the Mean
SPFi	Individual Subject Sun Protection Factor

	Document Name	207640 Protocol.doc		
	Type	Version	Document Identifier	Effective Date
	eldo_controlled	2.0; Most-Recent; Effective; CURRENT	090032d580d3df08	11-May-2017 13:45:31
	Reason For Issue	Auto Issue		

SPF	Sun Protection Factor
UV	Ultraviolet
UVA	Ultraviolet A
UVB	Ultraviolet B
W	Watt

[figure not shown]
13.2. Appendix 2 – Exclusion Criteria to be reassessed at Visit 2

1. PREGNANCY
Women who are known to be pregnant or who are intending to become pregnant over the duration of the study

2. BREAST-FEEDING
Women who are breast-feeding or lactating

3. CONCURRENT MEDICATION/ MEDICAL HISTORY

 C. Subjects with dermatological conditions E. Subjects who are tanned or have had sun exposure on the back area in the previous 4 weeks prior to screening F. Subjects having marks, blemishes or nevi or presenting existing sun damage in the test area I. Subjects with a non-uniform skin colour or hyperpigmentation in the test area

eldo clinical doc	1.0; CURRENT; Most-Recent; Effective	090032d580dcf91b	(8-Dec-2017 11:01:02
Reason For Issue	Imported as Effective from Legacy System		

GSK Consumer Healthcare Confidential Page 3
Statistical Analysis Plan Forte/207640

	4.3	Listings	13
	4.4	Top line Outputs	14
5	Appei	ndix 2:	15
	5.1	Templates for the Tables, Listings and Figures	15

Document Name	16.1.7 Documentation of statistical methods.pdf		
Туре	Version	Document Identifier	Effective Date
eldo clinical doc	1.0; CURRENT; Most-Recent; Effective	090032d580dcf91b	(8-Dec-2017 11:01:02
Reason For Issue	Imported as Effective from Legacy System		

GSK Consumer Healthcare Confidential Page 4
Statistical Analysis Plan Forte/207640

The purpose of this Statistical Analysis Plan (SAP) is to describe the planned analyses and output to be included in the Clinical Study Report for Clinical Study Protocol (CSP) 207640. This SAP will be finalized prior to database freeze and treatment code un-blinding.

1 Study details

An important parameter of efficacy for sunscreen products is the Sun Protection Factor (SPF). The SPF is a measure of how much solar energy (UV radiation) is required to produce sunburn on protected skin (i.e. in the presence of sunscreen) relative to the amount of solar energy required to produce sunburn on unprotected skin. In this study, the SPF is to be determined according to the International Standards Organization (ISO) 24444:2010 methodology (In vivo determination of the sun protection factor).

General safety and tolerability will be assessed based on the frequency and severity of Adverse Events (AEs).

1.1 Study design

Overall Design

A single-center, randomized, evaluator blind, intra-individual comparison, no treatment and positive controlled clinical study to determine the SPF of Physiogel Daily Defence Protective Day Cream Light as per ISO 24444:2010.

The provisional minimal erythemal dose of unprotected skin (MEDu) for each subject will be determined before starting the main test in order to center the UV dose ranges for the exposures of MEDu and MEDp. As the first step, a virgin area of skin on the back will be exposed to a preliminary series of UV exposures. The location of the irradiated test site for the provisional MEDu measurement will be randomised for all subjects. In this study, there will be a total of four irradiated test sites. Two test sites will be located below the scapula line, either side of the spine. The remaining two areas will be located below these sites and above the waist.

Six exposure sub-sites positioned within the randomised test area and centered on the estimated MEDu will be exposed to incremental UV doses using a geometric progression of 1.25. The dose of UV radiation administered will be chosen so that the estimated MEDu will be irradiated at the 4th of the 6 sub-sites. The estimated MEDu will be predicted based on the subject's mean Individual Typology Angle (ITA°) value. As the second step, a trained evaluator will assess the irradiated sub-sites for signs of unambiguous erythema 16-24 hours after UV exposure to determine the provisional MEDu. The provisional MEDu will be the lowest dose of UV radiation that produces the first perceptible unambiguous erythema with defined borders appearing over most of the field of UV exposure.

Once the provisional MEDu for a subject has been determined, the three remaining test sites will be demarcated. The test product (Physiogel Daily Defence Protective Day Cream Light) and positive control (P3 reference sunscreen formulation) will be applied to two of the three virgin test sites. The other test site will remain unprotected. The order of product application

Document Name	16.1.7 Documentation of statistical methods.pdf		
Туре	Version	Document Identifier	Effective Date
eldo clinical doc	1.0; CURRENT; Most-Recent; Effective	090032d580dcf91b	(8-Dec-2017 11:01:02
Reason For Issue	Imported as Effective from Legacy System		

GSK Consumer Healthcare Confidential Page 5
Statistical Analysis Plan Forte/207640

(test product, reference product and unprotected test site) will be randomised over the entire test group. Once the test product and positive control have been applied to the assigned test sites, the subject will undergo a second series of incremental UV exposures. For the unprotected site, the range of UV doses administered shall be selected using the subject's provisional MEDu. Six exposure sub-sites centered on the provisional MEDu shall be exposed with incremental UV doses using a geometric progression of 1.25. The dose of UV radiation administered to subjects will be chosen such that the provisional MEDu will be irradiated at the 4th of the 6 sub-sites. For the product protected sites, the UV doses administered shall be selected using the subject's expected MEDp, which is the multiple of the provisional MEDu for the subject and the expected SPF of either the test product (21) or reference sunscreen formulation (16). A minimum of 6 sub-sites centered on the expected MEDp shall be exposed with incremental UV doses using a geometric progression of 1.25. The dose of UV radiation administered to subjects will be chosen such that the expected MEDp will be irradiated at the 4th of the 6 subsites.

The minimum number of valid individual SPF (SPFi) results shall be 10 and the maximum number of valid SPFi results shall be 20. In order to achieve between 10 and 20 valid results, a maximum of five individual invalid results may be excluded from the calculation of the mean SPF. Consequently the actual number of test subjects used will fall between a minimum of 10 and a maximum of 25 subjects (i.e. a maximum of 20 valid results plus 5 rejected invalid results).

The study will include subjects of more than one Fitzpatrick phototype (I, II or III). It will not be permitted to adjust the expected SPF of the test product from subject to subject.

Visit 1 – Subject Screening

The following assessments will be conducted:

- 1. Informed Consent
- 2. Demographics
- 3. Medical History
- 4. Current / Concomitant Medication
- 5. ITA° Measurement
- 6. Fitzpatrick Skin Type Assessment
- 7. In/Exclusion Criteria
- 8. Subject Eligibility

Visit 2 – Provisional MED Irradiation (UV Exposure)

The following assessments will be conducted:

- 1. Current / Concomitant Medication*
- 2. Continued Eligibility*
- 3. Exclusion Criteria*
- 4. Subject Eligibility*
- 5. Randomisation
- 6. Provisional Minimum Erythemal Dose (MED) Irradiation
- 7. Adverse Events
- *Not required if Visit 2 is combined with Visit 1

Document Name	16.1.7 Documentation of statistical methods.pdf		
Туре	Version	Document Identifier	Effective Date
eldo clinical doc	1.0; CURRENT; Most-Recent; Effective	090032d580dcf91b	(8-Dec-2017 11:01:02
Reason For Issue	Imported as Effective from Legacy System		

GSK Consumer Healthcare Confidential Page 6
Statistical Analysis Plan Forte/207640

Visit 3 – Provisional MED Evaluation

The following assessments will be conducted:

- 1. Current / Concomitant Medication
- 2. Continued Eligibility
- 3. Visual Grading of Exposure Sub-Sites (Test Sites)*
- 4. Adverse Events
- *Visual grading of skin must occur 16-24 hours after completion of the Provisional MED Irradiation procedure

Visit 4 – Test Irradiation (UV Exposure)

The following assessments will be conducted:

- 1. Current / Concomitant Medication*
- 2. Continued Eligibility*
- 3. Test Product and Reference Sunscreen Application to Randomly Assigned Test Sites on the Back
- 4. UV Exposure of Test Product Treated, Reference Sunscreen Formulation Treated and Unprotected Test Sites
- 5. Adverse Events
- *Not required if Visit 4 is combined with Visit 3

Visit 5 – MEDp and MEDu Determination and SPF Calculation for Test and Reference Sunscreen

The following assessments will be conducted:

- 1. Current / Concomitant Medication
- 2. Continued Eligibility
- 3. Visual Grading of Exposure Sub-Sites to Determine MEDp and MEDu and calculate SPF*
- 4. Adverse Events
- 5. Subject Discharge from Study
- * Visual grading of skin must occur 16-24 hours after completion of the Test Irradiation procedure

1.2 Study objectives

Objectives	Endpoints
Primary Objective	Primary Endpoint
To determine the Sun Protection Factor of the test product	Arithmetic mean of all valid individual sun protection factor (SPFi) values; where SPFi = Minimal Erythemal Dose of product treated (MEDp) test sites in relation to unprotected (MEDu) test sites 16-24 hours after exposure to ultraviolet (UV) radiation.
Secondary Objectives	Secondary Endpoints
To evaluate the general safety of the test product	Frequency and severity of Adverse Events.

Document Name	16.1.7 Documentation of statistical methods.pdf		
Туре	Version	Document Identifier	Effective Date
eldo clinical doc	1.0; CURRENT; Most-Recent; Effective	090032d580dcf91b	(8-Dec-2017 11:01:02
Reason For Issue	Imported as Effective from Legacy System		

GSK Consumer Healthcare Confidential Page 7
Statistical Analysis Plan Forte/207640

1.3 Treatments

	Test Product	Reference Product	
Product Name	Physiogel Daily Defence Protective Day Cream Light	P3 Standard	
Product Formulation Code (MFC)	CCI	Commercially Available	
Expected SPF	21	16	
Application Quantity	$2.00 \pm 0.05 \text{ mg} / \text{cm}^2$	$2.00 \pm 0.05 \text{ mg} / \text{cm}^2$	
Route of Administration	Topical	Topical	

1.4 Timepoints and visit windows

Deviations from the scheduled assessment times must be avoided. The following are the assessment time windows.

Visit	Time window
Visit 2	0-7 days after Visit 1 (allowed to be combined with Visit 1)
Visit 3	1 day after Visit 2
Visit 4	0-7 days after Visit 3 (allowed to be combined with Visit 3)
Visit 5	1 day after Visit 4

Visual grading of skin at Visit 3 must happen 16-24 hours after irradiation at Visit 2. Visual grading of skin at Visit 5 must happen 16-24 hours after irradiation at Visit 4.

2 Data analysis

Data analysis will be performed by inVentiv Health Clinical. Prior to database hard lock a Blind Data Review Meeting (BDRM) will be conducted in which various aspects of the trial will be discussed and agreed. The statistical analysis software used will be SAS® version 9.4.

All listings will be produced for all randomised subjects, unless otherwise specified.

2.1 Populations for analysis

2.1.1 Subject disposition

Screen failures will be defined as subjects who consent to participate in the study but are never subsequently randomised. A summary will be provided of the number of subjects screened and the number of screen failures with reasons why subjects were not randomised (Table 14.1.1).

Document Name	16.1.7 Documentation of statistical methods.pdf		
Туре	Version	Document Identifier	Effective Date
eldo clinical doc	1.0; CURRENT; Most-Recent; Effective	090032d580dcf91b	(8-Dec-2017 11:01:02
Reason For Issue	Imported as Effective from Legacy System		

GSK Consumer Healthcare Confidential Page 8
Statistical Analysis Plan Forte/207640

Subject disposition will be summarized as the number and percentage of subjects (out of the number of randomised subjects) who complete the study, with the number who discontinue broken down by reason for discontinuation (Table 14.1.1). The table will also summarize the number and percentage of subjects assigned to each analysis population (refer to section 2.1.3).

2.1.2 Protocol violations

Protocol violations will be tracked by the study team throughout the conduct of the study. All violations will be reviewed prior to un-blinding and closure of the database to ensure all important violations are captured and categorised.

Major violations will be defined in the "Review Listing Requirement (RLR)" document.

A listing of protocol violations will be provided (Listing 16.2.1).

2.1.3 Analysis populations

Five populations are defined below.

Population	Definition / Criteria	Analyses Evaluated
All Screened	All subjects who are screened	Disposition
Subjects		
Randomised	All subjects who are randomised and	Protocol violations
	may or may not receive the application of	and data listings
	the study products.	
Safety	Safety population includes all subjects	Safety analysis
	who are randomised and receive any	
	application of the study products.	
Analysis	The analysis population includes those	SPF analysis
Population	randomised subjects who undergo	
	irradiation at Visit 4	

2.1.4 Subgroups/Stratifications

Not applicable.

2.1.5 Centers pools

Not applicable.

2.2 Patient demographics/other baseline characteristics

Demographic and baseline characteristics summaries will be produced for the safety and analysis population.

[figure not shown]
Document Name	16.1.7 Documentation of statistical methods.pdf		
Туре	Version	Document Identifier	Effective Date
eldo clinical doc	1.0; CURRENT; Most-Recent; Effective	090032d580dcf91b	(8-Dec-2017 11:01:02
Reason For Issue	Imported as Effective from Legacy System		

GSK Consumer Healthcare Confidential Page 9
Statistical Analysis Plan Forte/207640

2.2.1 Demographic characteristics

Categorical demographic variables include sex, race and Fitzpatrick skin type assessment. These variables will be summarized by the number and percentage of subjects with each relevant characteristic (Table 14.1.2.1 for safety, and Table 14.1.2.3 for analysis population). Age, individual typology angle (ITA°), meanL and meanB values will be summarized by the mean, standard deviation, median, minimum and maximum values. The demographics information age, sex, race, individual typology angle (ITA°), meanL and meanB values will be listed in Listing 16.2.4.1.

The Fitzpatrick scale is a numerical classification that is widely used by dermatologists to classify a person's skin type by their response to the sun exposure.

A tri-stimulus chromameter (Minolta CR 400, Langenhagen, Germany) which utilizes the L*, a*, b* colour space and complies with International Commission on Illumination (CIE) recommendations will be used to measure the colour of each subject's skin (dorsum). Four measurements will be taken on the back of each subject, between the waist and shoulder line, and the individual L* and b* values will be recorded as source data. The ITA° will be calculated and recorded on the case report form (CRF) as

calculated and recorded on the case re
ITA° ={
$$arc\ tangent\ [\frac{(L^*-50)}{b^*}]$$
} $\frac{180}{3.14159}$

2.2.2 General medical history

Medical history data will not be presented in the study report. A data listing will be produced at the blinded data review stage, for evaluation of protocol violations only.

2.2.3 Characteristics of Disease

Not applicable.

^{*}arc tangent is expressed in radians.

Document Name	16.1.7 Documentation of statistical methods.pdf		
Туре	Version	Document Identifier	Effective Date
eldo clinical doc	1.0; CURRENT; Most-Recent; Effective	090032d580dcf91b	8-Dec-2017 11:01:02
Reason For Issue	Imported as Effective from Legacy System		

GSK Consumer Healthcare Confidential Page 10
Statistical Analysis Plan Forte/207640

2.3 Treatments (study drug, rescue medication, other concomitant therapies, compliance)

2.3.1 Study Product/drug Compliance and Exposure

Any protocol violations associated with treatment applications will be listed at the blinded data review stage. Any protocol violations leading to exclusion from analysis population will be listed in the Listing 16.2.2.

2.3.2 Concomitant medication

Prior and concomitant medication/non-drug treatments data will be listed in the Listing 16.2.4.2. A data listing will also be produced at the blinded data review stage, for evaluation of protocol violations.

2.4 Analysis of Sun Protection Factor (SPF)

2.4.1 Primary efficacy endpoint

2.4.1.1 Primary endpoint definition

The primary analysis will be based on sun protection factor (SPF). Individual SPF for each subject (SPFi) is defined as the ratio of his/her minimal erythemal dose of protected skin (MEDp) over unprotected skin (MEDu), i.e., SPFi = MEDp / MEDu (keeping 1 decimal place for individual SPF). As each subject will have both test product and reference product applied on two sites of dorsum together with an unprotected site, each subject will provide two individual SPFs, one for the test product, one for the reference product. The MEDp at two protected sites and MEDu at the unprotected site of each subject determined by a trained grader at Visit 5 will be used in primary analysis.

Summary statistics for SPF, including mean, standard deviation, will be presented by treatment. The 95% CIs for the mean SPFs of the two treatments will be constructed via t-statistic and presented together with summary statistics (Table 14.2.1.1. for Analysis Population). The study will be considered valid if

- the range of the 95% CI of the mean SPF is within ±17% of the mean SPF for each product;
- The mean SPF of the reference sunscreen formulation (P3) used in the test shall fall within the defined acceptance limits (lower limit, SPF 13.7; upper limit, 17.7).

2.4.1.2 Statistical hypothesis, model, and method of analysis

Except the 95% CI for mean SPF, there is no formal statistical inference to be performed.

2.4.1.3 Supportive analyses

Not applicable.

Document Name	16.1.7 Documentation of statistical methods.pdf		
Туре	Version	Document Identifier	Effective Date
eldo clinical doc	1.0; CURRENT; Most-Recent; Effective	090032d580dcf91b	(8-Dec-2017 11:01:02
Reason For Issue	Imported as Effective from Legacy System		

GSK Consumer Healthcare Confidential Page 11
Statistical Analysis Plan Forte/207640

2.4.2 Secondary efficacy endpoint

Not applicable.

2.4.3 Handling of missing values/censoring/discontinuations

Missing data will not be replaced or imputed.

2.5 Analysis of secondary objectives

Not applicable.

2.6 Safety

2.6.1.1 Adverse events and Serious Adverse Events

All adverse events (AEs) will be summarised by primary system organ class and preferred term

Treatment emergent adverse events (TEAEs), defined as the AEs reported after study product application, will be summarized by the number and percentage of subjects having any adverse event, any adverse event in each System Organ Class, and and the number of occurrences of each individual adverse event (Table 14.3.1.1). All TEAEs will also be tabulated by severity (Table 14.3.1.2). Treatment emergent AEs suspected of a relationship to study medication will be presented in a similar manner (Table 14.3.1.3). For treatment related AEs, these will also be presented by severity (Table 14.3.1.4).

Deaths occurring during treatment (if any) will be listed (Listing 14.3.2.1) by treatment, including the date and study day of death, and the principal cause of death. Non-fatal serious adverse events causing study treatment discontinuation will be listed (Listing 14.3.2.2).

AEs will be collected from the start of provisional MEDu irradiation procedure until 5 days after the last administration of the study product. SAEs however, if assessed as related to study participation or related to a GSK concomitant medication will be recorded from the time a subject consents to participate in the study up to and including any follow-up contact. All AEs will be listed in Listing 16.2.7.1 for randomised subjects and Listing 16.2.7.2 for non-randomised subjects.

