
 1. Current / Concomitant Medication* 2. Continued Eligibility* 3. Test Product and Reference Sunscreen Application to Randomly Assigned Test Sites on the Back 4. UV Exposure of Test Product Treated, Reference Sunscreen Formulation Treated and Unprotected Test Sites. 5. Adverse Events 
*Not required if Visit 4 is combined with Visit 3

Visit 5 – MEDp and MEDu determination and SPF calculation for test and reference sunscreen

The following assessments will be conducted:
 
 1. Current / Concomitant Medication 2. Continued Eligibility 3. Visual Grading of Exposure Sub-Sites to Determine MEDp and MEDu and calculate SPF* 4. Adverse Events 5. Subject Discharge from Study 
* Visual grading of skin must occur 16-24 hours after completion of the test irradiation procedure

Type and Planned Number of Subjects

Healthy volunteers aged between 18-70 years (inclusive) with Fitzpatrick phototype I, II or III, an ITA° value greater than 28° and who are untanned on the test area will be recruited for this study. The study will contain a population of subjects of more than one Fitzpatrick phototype.

To complete the study successfully, the minimum number of valid individual sun protection factor (SPFi) results will be 10 and the maximum number of valid SPFi results will be 20 for both the test product and positive control. In order to achieve between 10 and 20 valid SPFi results, a maximum of 5 individual invalid results may be excluded from the calculation of the mean SPF. Consequently, the actual number of subjects used for the study will fall between a minimum of 10 and a maximum of 25 (i.e. a maximum of 20 valid SPFi results plus 5 rejected invalid results).

In order to determine the number of test subjects, the 95% confidence interval (95% CI) of the mean SPF shall be taken into account. A minimum of 10 subjects shall be tested. The test shall be considered valid for the first 10 subjects if the resulting range of the 95% CI of the mean SPF is within ±17% of the mean SPF. If it is not within ±17% of the mean SPF, the number of subjects shall be increased stepwise from the minimum number of 10 until the 95% CI statistical criterion is met (up to a maximum

 GlaxoSmithKline	Document Name	207640 Protocol.doc		
	Type	Version	Document Identifier	Effective Date
	eldo_controlled	2.0; Most-Recent; Effective; CURRENT	090032d580d3df08	11-May-2017 13:45:31
	Reason For Issue	Auto Issue		

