
5. Randomisation
 
6. Provisional Minimal Erythema Dose (MED) Irradiation
 
7. Adverse Events
 
*Not required if Visit 2 is combined with Visit 1

Visit 3 – Provisional MED Determination
 
The following assessments will be conducted:
 
 1. Current / Concomitant Medication 2. Continued Eligibility 3. Visual Grading of Exposure Sub-Sites (Test Sites)* 4. Adverse Events 
*Visual grading of skin must occur 16-24 hours after completion of the Provisional MED Irradiation procedure

Visit 4 – Test Irradiation (UV Exposure)
 
The following assessments will be conducted:
 
 1. Current / Concomitant Medication* 2. Continued Eligibility* 3. Test Product and Reference Sunscreen Application to Randomly Assigned Test Sites on the Back 4. UV Exposure of Test Product Treated, Reference Sunscreen Formulation Treated and Unprotected Test Sites. 5. Adverse Events 
*Not required if Visit 4 is combined with Visit 3

Visit 5 – MEDp and MEDu determination and SPF calculation for test and reference sunscreen
 
The following assessments will be conducted:
 
 1. Current / Concomitant Medication 2. Continued Eligibility 3. Visual Grading of Exposure Sub-Sites to Determine MEDp and MEDu and calculate SPF* 4. Adverse Events 5. Subject Discharge from Study 
* Visual grading of skin must occur 16-24 hours after completion of the test irradiation procedure

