7.4. Reporting Adverse Events and Serious Adverse Events

AE Reporting to GSKCH:

 1. AEs will be recorded in the AE section of the CRF. 2. Medical conditions recorded by the subject on a diary card or similar document that meet the definition of an AE must also be recorded in the AE section of the CRF, if not previously well-characterized by the investigator in the subject’s medical history. 3. AEs elicited by the investigator in a standard manner at the study visits should also be recorded in the AE section of the CRF. The investigator or designee

 GlaxoSmithKline	Document Name	207640 Protocol.doc		
	Type	Version	Document Identifier	Effective Date
	eldo_controlled	2.0; Most-Recent; Effective; CURRENT	090032d580d3df08	11-May-2017 13:45:31
	Reason For Issue	Auto Issue		

must ask the subject the following question during each visit including any follow-up visits: ***“Have you felt unwell, experienced any symptoms or taken any medication (since your last visit) (today) (since your last dose) (since the last session)?”***

4. The medically qualified investigator should review adverse events in a timely manner; this review should be documented in writing in the source document or in the CRF.
5. After the study is completed at a given site, and the site has received their study data on Compact Discs (CDs), the electronic data collection tool will be removed from the internet to prevent the entry of new data or changes to existing data.

SAE Reporting to GSKCH:

A paper copy of the SAE form provided in the investigator study master file should be completed as fully as possible.

It is essential to enter the following information:

1. Protocol and subject identifiers
2. Subject’s demography
3. Description of events, with diagnosis if available
4. Investigator opinion of relationship to study product (see section 8.3)
5. Criterion for seriousness.

The following are desirable and are of particular relevance for investigator and GSKCH assessment of the SAE report:

1. Date of onset of AE
2. Date AE stopped, if relevant
3. Study product start date
4. Study product end date if relevant
5. Action taken on study product
6. Outcome if known

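### The SAP defines treatment-emergent AEs by time of reporting, not onset, so when Visits 3 and 4 are on separate days, events from the 0-7 days before product application can be counted as treatment-emergent

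*SAP*

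**What the plan says.** SAP 2.6.1.1 gives the only rule: "Treatment emergent adverse events (TEAEs), defined as the AEs reported after study product application". It sets no condition on when the event began, and no such condition appears elsewhere in the SAP or the protocol.

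The same section starts collection before any product is used: "AEs will be collected from the start of provisional MEDu irradiation procedure until 5 days after the last administration of the study product". Protocol 7.2 gives the same period.

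SAP 1.4 places Visit 4 "0-7 days after Visit 3 (allowed to be combined with Visit 3"). In Protocol 3.1 the Visit 4 list has "3. Test Product and Reference Sunscreen Application to Randomly Assigned Test Sites on the Back", followed by "UV Exposure of Test Product Treated, Reference Sunscreen Formulation Treated and Unprotected Test Sites. 5. Adverse Events". The synopsis, SAP 1.1 and the order of Protocol 6.4.3 to 6.4.5 agree. Footnote 2 of the Schedule of Events waives the Visit 4 AE assessment when the visit is combined with Visit 3.

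The scripted AE question in Protocol 7.4 begins "Have you felt unwell, experienced any symptoms or taken any medication (since your last visit") and then offers three other time frames: today, since the last dose, and since the last session.

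**The concern.** AE collection starts at the Visit 2 irradiation, so every subject has a pre-product AE period by design. The TEAE definition is the only rule that separates it from the post-product period. A rule based on reporting time does this correctly only if each pre-product event is reported before application, and the listed Visit 4 order does not ensure that.

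The safety endpoint is the frequency and severity of AEs for the test product. SAP 2.6.1.1 says that all AEs will be summarised, but the table list in SAP 4.2 contains only the four TEAE tables (14.3.1.1 to 14.3.1.4). Those tables are therefore the only tabulated frequency and severity results, and Table 14.3.1.1 is also a top-line output. An event that predates the product could be shown there as treatment-emergent while Listing 16.2.7.1 shows its onset before study day 1, the day of first treatment.

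**Working it through.** **Inputs**

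- Visit 3 is 1 day after Visit 2, Visit 4 is 0-7 days after Visit 3, and Visit 5 is 1 day after Visit 4 (SAP 1.4).
- Product is applied once, at Visit 4 (Protocol 6.4.3).
- AE collection ends 5 days after the last application (Protocol 7.2, SAP 2.6.1.1).
- The AE step at Visit 4 is listed after application and irradiation. I take this order as followed and the question as reaching back to Visit 3.
- At most 25 subjects are randomised (Protocol 4.5).
- The background AE rate is not given in the documents. I assume that it is constant over time.

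**Step 1: the pre-product look-back.** Let g = Visit 4 minus Visit 3. Running through all permitted calendars gives g = 0 to 7 days, which reproduces the SAP's window. An event that began between Visits 2 and 3 should be reported at Visit 3. If it is missed there, the outer limit is 1 + 7 = 8 days before product.

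**Step 2: one event followed through.** Take Visit 3 on day 0 and Visit 4 on day 7. A cold begins on day 1. Product is applied on day 7, and the AE question is asked later that day.

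- Reporting rule (SAP as written): the cold is reported after application, so it is a TEAE.
- Onset rule: the cold began 6 days before application, so it is not a TEAE.

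The same contrast arises if the cold is first mentioned at Visit 5.

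**Step 3: share of background events.** With a constant rate, events are proportional to days at risk. Among background events counted as TEAEs, the share that predates the product is

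share = g / (g + 5)

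| Gap g (days) | Calculation | Pre-product share |
|---|---|---|
| 0 (combined visits) | 0/5 | 0% |
| 1 | 1/6 | 17% |
| 3 | 3/8 | 38% |
| 5 | 5/10 | 50% |
| 7 | 7/12 | 58% |

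These figures take every event from the gap to be first reported at the Visit 4 AE step or later. Any event that surfaces before application lowers the share.

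**Step 4: after the correction.** With an onset rule, the pre-product time inside the TEAE window falls from 0-7 days to 0. The exception is the part of the Visit 4 date before application, where application time is not recorded.

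**The case against.** The strongest case against has five parts.

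1. **The order is inferred.** The Visit 4 items are a numbered list of assessments, and no sentence makes the sequence binding. Concomitant medication and continued eligibility come before application, so some illnesses may surface then. Protocol 7.4 also offers several time frames for the question and does not assign one to Visit 4. This stands: the documents do not show that the question is always asked after application. They do not require it before application either, and the period since Visit 3 is within the collection period and has to be covered somehow.

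2. **Combined visits are exempt.** This stands. The gap is then zero, and the documents do not say how many subjects will have separate visits.

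3. **A larger share is tempting but not supported.** Counting follow-up only to Visit 5 would give 7/(7+1) = 88%. Both documents collect AEs for 5 days after application, so the plan's own window gives 58% at the longest gap.

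4. **Visit 2 irradiation reactions.** A reader might infer that the TEAE tables would routinely absorb these. Visit 3 has its own AE assessment the day after that irradiation and before any product, and Protocol 7.1.1 excludes localised UV erythema from AEs. Only delayed or missed reactions of other kinds remain.

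5. **Existing safeguards.** The protocol plans only a by-subject listing (9.3.3), and Listing 16.2.7.1 shows onset for each event. Protocol 7.3 requires causality assessment to consider timing, so Tables 14.3.1.3 and 14.3.1.4 should mostly screen such events out. The error runs towards over-counting. All this limits the harm, but Tables 14.3.1.1 and 14.3.1.2 do not depend on causality and stay exposed.

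**Conclusion.** The definition is wrong as written: it uses reporting time where onset is needed. Its effect is conditional. It arises when Visits 3 and 4 are on separate days and AEs are elicited in the listed order, or when an earlier event is first mentioned at Visit 5.

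Under the constant-rate assumption and the 5-day post-application window, the misclassified share of background events runs from 0 to about 58%, depending on the gap. These are shares, not predicted counts. With at most 25 subjects the absolute numbers may be small.

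The documents do not support reading this as a threat to the trial's main result. SPF is unaffected, and no formal inference is planned beyond the confidence interval for mean SPF. It is a correction that should be made to the safety tables.

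**What to change.** In SAP 2.6.1.1, define TEAEs as AEs with onset on or after the date of study product application at Visit 4. For events that start on that date, compare onset time with application time where the latter is recorded; otherwise count them as treatment-emergent. Add pre-existing AEs recorded as worsening after application, where the CRF captures this. Derive the flag from the start date, start time and study day in Listing 16.2.7.1, and keep pre-application events in the listing of all AEs.

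The two qualifications are needed because the documents do not show that the finer data exist. The log in Protocol 5.9.1 holds dates and quantities, no SAP listing template shows application time, and Listing 16.2.7.1 has one intensity entry per event. A strict date-and-time rule with a mandatory worsening limb could therefore need data that are not captured.

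The cost is a short wording change and one derivation; the date rule needs no new data. The downside is that TEAE counts may fall slightly.
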